Protocol

**Title:** Skin Adhesive Glue versus Skin Stapling Comparing  
CLOSure Effectiveness in Colorectal Cancer Surgery  
(CLOSE Trial)

**Investigational product:** 2-octyl cyanoacrylate (Leukoplast® Skin Adhesive, Chemence medical, Inc., USA)

**Protocol number:** NCT 06549803

**Study design:** A multicenter, non-inferiority, randomized controlled trial with two parallel comparison arms.

**Number of participating centers:** 3 centers of tertiary hospitals in South Korea (the Catholic Colorectal group)

STUDY PROTOCOL

From March 2022

Version 1.0

## 1. Background

Surgical site infection (SSI) represents one of the most common and costly postoperative complications following colorectal surgery, with reported incidence rates ranging from 4% to 15% depending on patient and procedural factors. SSI prolongs hospitalization, increase healthcare costs, and is associated with reduced patient quality of life. Optimizing skin closure technique is a potentially modifiable determinant of SSI risk.

Skin stapling devices have long been the standard method for fascial and skin closure in abdominal surgery due to their speed, ease of application, and secure wound apposition. However, stapled wounds have been associated with greater postoperative pain, visible scarring, the need for subsequent staple removal, and in some series, higher SSI rates compared with suture-based alternatives.

Skin adhesives, including 2-octyl cyanoacrylate formulations (e.g., Leukosan Adhesive), form a flexible, watertight microbial barrier within seconds of application, eliminating the need for suture or staple removal and potentially reducing pain and improving cosmesis. Retrospective data have suggested that skin adhesive may be associated with lower SSI rates and reduced wound care costs compared with skin staples in colorectal procedures. However, prospective randomized controlled evidence comparing the two approaches specifically with respect to SSI incidence and cost-effectiveness in the laparoscopic colorectal cancer setting is currently absent from the literature.

This trial is designed to address this evidence gap by directly comparing skin adhesive with conventional skin stapling in patients undergoing elective laparoscopic or robotic colorectal cancer surgery at three high-volume tertiary referral centers.

## 2. Objectives

### 2.1 Primary objective

To demonstrate the non-inferiority of 2-octyl cyanoacrylate skin adhesive compared with conventional skin stapling with respect to the incidence of SSI within 30 days of surgery, assessed at the time of hospital discharge. SSI is defined according to Centers for Disease Control and Prevention criteria and includes both superficial incisional SSI and deep incisional SSI.

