### 2.2 Secondary objective

To compare postoperative pain intensity (VAS score, 0-10) at postoperative days 1 and 3.

To compare length of hospital stay.

To compare the incidence of major postoperative complications within 30 days

To compare total operative times (minutes).

To compare total wound-related cost-effectiveness between the two groups, including device cost and wound dressing service cost.

To assess wound healing quality and patient satisfaction via a validated questionnaire administered at the outpatient clinic visit one week after discharge.

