### **3.5 Blinding**

This was an open-label trial; patients and clinicians were not blinded. However, outcome assessors were blinded to treatment assignment. Physicians performed postoperative wound assessment on the day of discharge, and statistical analyses were conducted without knowledge of group assignment until completion.

The open-label design was necessary due to the visibly distinct nature of the interventions. To minimize potential independent clinical nurse specialists, not involved in surgery or allocation, conducted wound evaluations and patient satisfaction surveys.

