### **3.6. Outcomes**

#### **3.6.1 primary Endpoint**

Incidence of SSI (superficial or deep incisional) within 30 days of surgery.

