#### **3.6.2 Secondary Endpoints**

Outcomes	Measurement Tool	Time point
Pain score	Visual Analogue Scale (VAS, 0-10)	POD1, 2, and 3
Length of hospital stay	Day from surgery to discharge	At discharge
Operative time	Minutes (skin incision to wound closure)	Intraoperative
Major complications	Clavien-Dindo classification	Within 30 days
Cost effectiveness	Dressing supply cost, dressing service cost, Dressing frequency	Until discharge
Patient satisfaction and wound quality	Validated wound questionnaire, investigator wound assessment	1 week postop discharge OPD visit

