## 4. Study Schedule

		Study Period						
		Enrollment	Allocation	Post-allocation				Close-out
	Time point	-2 to 0 day	Operation day	Postoperative day 1	Postoperative day 2	Postoperative day 3	Discharge	First OPD f/u
Enrollment	Eligibility screen	O						
	Informed consent	O						
	Randomization		O					
	Allocation		O					
Intervention	Experimental intervention		O					
	Control intervention		O					
Assessment	Demographical data	O						
	Medical history	O						
	Laboratory	O	O		O		O	
	Parameters of surgical procedure		O					
	VAS score		O	O	O	O		
	Documentation of SSI		O	O	O	O		O
	Documentation of other complication		O	O	O	O		O
	Length of hospital stay							O
	readmission							O
	Patient questionnaire							O
	Pathologic results							O
	Cost outcomes							O

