## 5.3. Adverse Event Reporting

All adverse events will be recorded from the time of randomization through the 30-day follow-up visit. Serious adverse events (SAEs) will be reported to the IRB within 24 hours of the investigator's awareness and managed according to institutional and national regulatory guidelines.

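### The protocol contradicts itself on when the primary endpoint is ascertained, and no scheduled contact covers the time from the first outpatient visit to day 30

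*Protocol*

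**What the plan says.** Five places in the protocol bear on when surgical site infection (SSI) is measured.

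- Section 2.1 (primary objective): "incidence of SSI within 30 days of surgery, assessed at the time of hospital discharge".
- Section 3.5 (blinding): "Physicians performed postoperative wound assessment on the day of discharge".
- Section 3.6.1 (primary endpoint): "Incidence of SSI (superficial or deep incisional) within 30 days of surgery", with no mention of discharge.
- Section 4 (schedule): the row "Documentation of SSI" is marked on the operation day, on postoperative days 1 to 3 and at the first outpatient follow-up, which is the close-out column. The discharge cell of that row is blank in the text as extracted. There is no day-30 column.
- Section 5.3 (adverse events): events are recorded "from the time of randomization through the 30-day follow-up visit".

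The outpatient visit is timed in section 2.2, where the questionnaire is "administered at the outpatient clinic visit one week after discharge", and again in the table of section 3.6.2 ("1 week postop discharge OPD visit"). Major complications are also a 30-day endpoint in sections 2.2 and 3.6.2, and the schedule row for other complications has the same marks as the SSI row.

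**The concern.** An assessment made at discharge cannot count an infection that appears after discharge, so section 2.1 cannot be carried out as worded. A site that follows 2.1, one that follows the schedule and one that follows 5.3 would stop looking for the primary event at three different times.

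The primary comparison uses a fixed absolute margin of 0.99 percentage points (sections 3.8 and 3.9). If some 30-day events are not seen, both observed rates and their difference shrink, but the margin does not. The stated error rate and power then no longer describe the 30-day question. An infection that was never looked for cannot be recovered in the analysis.

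**Working it through.** **1. The passages side by side**

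| Source | Last point at which SSI is assessed |
|---|---|
| 2.1, 3.5 | Day of discharge |
| 4, with 2.2 and 3.6.2 | First outpatient visit, one week after discharge |
| 3.6.1 | Day 30 (window only, no visit named) |
| 5.3 | A 30-day visit, for adverse events, absent from section 4 |

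If the patient is discharged on day L, the outpatient visit falls at about day L + 7. It reaches day 30 only if L is at least 30 − 7 = 23 days. The protocol gives no expected length of stay, so the length of the uncovered interval is unknown. It is empty only for stays of about three weeks or more.

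**2. The plan's own figure**

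Inputs from section 3.8 and its software output: control rate pC = 0.058, adhesive rate pT = 0.010, margin D0 = 0.0099, one-sided alpha 0.025, power 80%, unpooled Z.

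n = [pC(1−pC) + pT(1−pT)] × (1.960 + 0.842)² / (D0 − D1)², with D1 = 0.010 − 0.058 = −0.048

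= (0.054636 + 0.0099) × 7.849 / 0.0579² = 151.1, hence 152 per group. Power at 152 is 0.8023, as stated. The sample size reproduces.

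**3. Equal capture in both arms**

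Let f be the share of 30-day SSIs that is ascertained. The protocol gives no value, so f is an assumption. The observed rates become f·pT and f·pC, with the margin kept at 0.0099. This also assumes that 5.8% is a fully ascertained 30-day rate; section 3.8 states no window for it.

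The probability that the upper limit of the Wald 95% interval lies below 0.0099 was obtained by exact binomial enumeration with 152 per arm:

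| f | Truth at the margin (6.79% vs 5.8%) | Planning rates (1.0% vs 5.8%) |
|---|---|---|
| 1.00 | 2.6% | 87% |
| 0.75 | 3.5% | 81% |
| 0.50 | 5.7% | 74% |

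The 87% at f = 1 is the exact counterpart of the protocol's 80.2%, which is a normal approximation. By that approximation the planning-rate column reads 80.2%, 72.4% and 63.2%, and the margin column reads 2.5%, 3.2% and 4.3%. The pattern is the same.

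**4. Unequal capture, truth at the margin**

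- Adhesive 75%, staples 90%: observed rates 0.75 × 6.79% = 5.09% and 0.90 × 5.8% = 5.22%. The chance of a claim is 6.7%.
- Adhesive 90%, staples 75%: observed rates 6.11% and 4.35%. The chance of a claim is 1.3%.

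**The case against.** A reader might infer that late infections are missed and that the result is pushed towards non-inferiority. The protocol does not support either statement in that form.

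**Are late cases lost?** Section 5.1 lists superficial and deep incisional SSI as an anticipated adverse event, and section 5.3 records adverse events to a 30-day visit. That is a possible route for late cases. It stands as a reason to say that capture is not assured, rather than that it fails. It does not settle the matter, because a visit named only under adverse-event reporting and absent from the schedule does not define how the primary endpoint is ascertained.

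**Is the direction known?** No. Equal under-capture raises the chance of a claim when the adhesive is truly equal or worse, but lowers it at the protocol's own planning rates. For unequal capture, stapled wounds have dressings and staple removal (section 3.3.2), while adhesive wounds receive no additional dressing (3.3.1), so extra detection in the stapling arm is plausible. But no passage says SSI is ascertained at those contacts, and the schedule is the same for both arms.

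**Is there no discharge assessment?** That reading rests on one blank cell in a table read by a program, and section 3.5 expressly places a wound assessment on that day. The blank cell is best described as a further conflict with 2.1 and 3.5. If it is an extraction loss, the missing day-30 contact and the conflict between 2.1, 3.6.1 and 5.3 remain.

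**Could this be left to a statistical analysis plan?** No. When patients are seen, and over what window the primary event is counted, are matters for the protocol.

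**Conclusion.** The contradiction is real, concerns the primary endpoint and needs correcting. Followed as written, SSIs and major complications between the first outpatient visit and day 30 have no scheduled endpoint assessment. That conclusion rests on the text alone.

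The numerical effect is a sensitivity range and not an estimate of bias. At capture shares of 75% and 50%, false non-inferiority at the margin is modestly raised or roughly doubled, and the chance of a claim at the planning rates drops by about 6 or 14 percentage points. With unequal capture the error can lie on either side of the nominal 2.5%. These figures depend on assumed capture shares, on 5.8% being a full 30-day rate and on the Wald interval.

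**What to change.** - In section 2.1, delete the clause that ties assessment to discharge.
- Define the primary endpoint once, as any superficial or deep incisional SSI from surgery to day 30, and use that definition in 2.1 and 3.6.1.
- In section 4, add an SSI entry at discharge, in line with 3.5, and add the day-30 contact that 5.3 already presupposes. It may be a clinic visit, a telephone call or a record check, but must be identical in both arms. Use it for SSI and for the 30-day complication endpoint.

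The cost is a protocol amendment and one short contact per patient.

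If the day-30 contact will not take place, restate the window consistently in 2.1, 2.2, 3.6 and 5.3 and drop the 30-day claim. Renaming the primary endpoint alone would not be enough: it would leave the 30-day complication endpoint and section 5.3 unreconciled. A window that ends at the first outpatient visit would also vary with length of stay, and the protocol should acknowledge this if that option is chosen.

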### 2.2 Secondary objective

To compare postoperative pain intensity (VAS score, 0-10) at postoperative days 1 and 3.

To compare length of hospital stay.

To compare the incidence of major postoperative complications within 30 days

To compare total operative times (minutes).

To compare total wound-related cost-effectiveness between the two groups, including device cost and wound dressing service cost.

To assess wound healing quality and patient satisfaction via a validated questionnaire administered at the outpatient clinic visit one week after discharge.

## 3. Methods

### 3.1 study design

This is a prospective, randomized, open-label, multicenter, non-inferiority trial. The trial is reported in

accordance with the standard protocol items

### 3.2. Eligibility Criteria

#### 3.2.1 Inclusion criteria

- 1) Adults patients aged 19-80 years
- 2) ASA physical status classification I –III
- 3) Histologically confirmed or clinically suspected colorectal adenocarcinoma scheduled for elective curative resection by laparoscopic or robotic surgery
- 4) Written informed consent provided prior to enrollment

#### 3.2.2 Exclusion criteria

- 1) Age over 80 years
- 2) Simultaneous resection of  $\geq 2$  abdominal organs
- 3) Known hypersensitivity to cyanoacrylate compounds
- 4) Uncontrolled diabetes mellitus
- 5) Emergency surgery
- 6) Inability or unwillingness to provide informed consent

### 3.3 Interventions

#### 3.3.1. Experimental group – Skin adhesive

Following fascial closure, the skin edges are approximately with subcutaneous absorbable sutures and the epidermal layer is sealed with 2-octyl cyanoacrylate skin adhesive (Leukosan Adhesive). The adhesive is applied in three thin layers with 30 second drying intervals per manufacturer instructions. No additional wound dressing is applied.

#### 3.3.2. Control group- conventional skin stapling

Following fascial closure, the subcutaneous layer is sutured by Vicryl and skin is approximately using a disposable skin stapler (Visistat Regular). Staples are placed at approximately 5mm intervals. Standard wound dressings are applied. Staples are removed at the discretion of the attending surgeon, typically a postoperative day 7-10.

### 3.4 Randomization

Randomization was performed using a computer-generated sequence created by the Department of Biostatistics at Seoul St. Mary's Hospital. Allocation was stratified by surgical approach (laparoscopic vs robotic-assisted) and tumor location (colon vs rectum). Within each stratum, block randomization with variable block sizes (4,6, and 8) ensured balance while minimizing predictability.

Allocation concealment was achieved through a centralized, web-based system managed by an independent biostatistician not involved in patient recruitment, enrollment, or outcomes assessment. Patients were randomized

the day before surgery in a 1:1 ratio to either the skin adhesive (Bond) or skin stapling (Stapler) group. Treatment allocation was concealed from all clinical staff until assignment.

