### 3.9 Statistical Analysis

All analyses will be performed using SPSS version 27.0 (IBM Corp) or R version 4.3 or later. The primary non-inferiority analysis will be conducted on both the per-protocol (PP) population and the intention-to-treat (ITT) population; non-inferiority will be claimed only if both analyses are concordant.

The primary endpoint (SSI rate) will be analyzed using a one-sided Z test for the difference in proportions, with the 95% confidence interval for the difference (skin adhesive minus stapling) reported. Non-inferiority will be concluded if the upper bound of the 95% confidence interval is below the pre-specified non-inferiority margin of 0.99 percentage points.

Continuous secondary endpoints (VAS, length of stay, operative time, cost) will be compared using the Student's t-test or Mann-Whitney U test as appropriate. Categorical variables (complication rates, patient satisfaction categories, pathological stage) will be analyzed using the chi-square test or Fisher's exact test. A two-tailed p-value of <0.05 will be considered statistically significant for all secondary comparisons.

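### Neither the stratified randomisation nor the tests in section 3.9 account for centre: a small loss for SSI, and a possibly larger loss of precision for length of stay, operative time and cost

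*Protocol*

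**What the plan says.** The Protocol's title page gives the number of sites as "3 centers of tertiary hospitals in South Korea". Section 3.4 names two stratification factors: "Allocation was stratified by surgical approach (laparoscopic vs robotic-assisted) and tumor location (colon vs rectum". It continues: "Within each stratum, block randomization with variable block sizes (4,6, and 8) ensured balance while minimizing predictability". That makes 2 × 2 = 4 strata, and the blocks within them run across all three hospitals. Allocation is central and web-based, and patients were randomised "the day before surgery in a 1:1 ratio to either the skin adhesive (Bond) or skin stapling (Stapler) group".

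Section 3.9 fixes the tests. For SSI: "The primary endpoint (SSI rate) will be analyzed using a one-sided Z test for the difference in proportions". For VAS, length of stay, operative time and cost, the groups "will be compared using the Student's t-test or Mann-Whitney U test as appropriate". Categorical outcomes get a chi-square or Fisher's exact test. None of these has a term for centre, or for approach and location.

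Some elements of care and outcome are left to local practice. In section 3.3.2, "Staples are removed at the discretion of the attending surgeon", and the control arm's dressings are described only as standard. Section 3.6.2 counts dressing costs and dressing frequency up to discharge, and length of stay is itself an endpoint.

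**The concern.** Blocking within approach-by-location strata balances the arms overall but not inside any one hospital. A hospital can by chance contribute noticeably more patients to one arm. If hospitals differ in SSI rate, discharge habits, operating time or dressing charges, that imbalance moves the observed arm difference, and the stated tests do nothing to remove it.

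What is at stake is precision. Centre is known for every patient. For endpoints that depend on site practice, leaving it out makes confidence intervals wider than they need be.

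**Working it through.** **The plan's own figure.** Inputs from section 3.8: control 5.8%, adhesive 1.0%, margin 0.99 points, one-sided alpha 0.025, power 80%, unpooled Z test.

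- n per arm = (1.960 + 0.842)² × (0.058 × 0.942 + 0.010 × 0.990) / (0.0099 + 0.048)² = 7.849 × 0.064536 / 0.003352 ≈ 151.1, so 152.
- Power at 152 per arm is 0.8023.

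Both agree with the protocol. Centre does not enter this calculation, and accounting for it would not change N.

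**Imbalance within a centre.** Assume three equal centres, about 101 of 304 patients each (the protocol gives no centre sizes).

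- SD of one arm's count in a centre = √[101 × 0.25 × (304 − 101)/303] = 4.11.
- SD of the arm difference in that centre = 2 × 4.11 = 8.2 patients.

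The stated scheme was also simulated, with blocks of 4, 6 and 8 in four strata, assumed stratum shares of 45/20/20/15%, and centres either equal or 60/25/15%. The largest within-centre arm difference had a median of 8–10 patients and a 95th percentile of 18–19.

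**Effect on the SSI difference.** With equal centres, the SD of the chance shift from centre mix is (2/√304) × SD of the centre rates = 0.1147 × SD. The SE below takes the same rate in both arms. All centre rates are assumptions.

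| Centre SSI rates | SD of rates | SD of shift | SE of arm difference |
|---|---|---|---|
| 4, 6, 8% | 1.63 points | 0.19 points | √(2 × 0.06 × 0.94/152) = 2.72 points |
| 4, 4, 15% | 5.19 points | 0.60 points | √(2 × 0.0767 × 0.9233/152) = 3.05 points |

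Centre's share of the variance is (shift SD / SE)²:

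- 4/6/8%: (0.19/2.72)² ≈ 0.5%. Removing it shortens the SE by about 0.2%.
- 4/4/15%: (0.60/3.05)² ≈ 4%. Removing it shortens the SE by about 2%.

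**Is this an error beyond the stated interval?** No. The binomial variance splits into a within-centre and a between-centre part. For 4/6/8%, the mean of p(1 − p) is 0.05613 and the variance of p is 0.00027. They sum to 0.0564 = 0.06 × 0.94, the per-patient variance that the unadjusted interval already uses.

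**Type I error.** Simulation with the true difference at the margin (5,000 runs per scenario, overall control rate 5.8%, centre rates equal or in ratio 1:2:3 or 1:3:6):

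- Unadjusted Z test: rejects in 2.7–3.2% of runs (2.8–2.9% with no centre differences).
- Centre-stratified Mantel-Haenszel test: rejects in 3.0–3.3%.

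The Monte Carlo SE is about √(0.03 × 0.97/5000) = 0.24 points, so centre makes no visible difference.

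**Length of stay, operative time and cost.** If centre explains a share R of the variance, adjustment multiplies the variance of the arm difference by about 1 − R. The protocol gives no R; the range is an assumption.

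- R = 5%: SE shorter by 1 − √0.95 = 2.5%. The unadjusted 304 patients are worth about 304 × 0.95 = 289.
- R = 20%: SE shorter by 1 − √0.80 = 10.6%. They are worth about 304 × 0.80 = 243.

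**The case against.** The case for leaving the plan alone is substantial.

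- **The design is defensible.** Central allocation with two prognostic stratification factors is unbiased and valid. This stands: the plan contains no contradiction, wrong figure or invalid test on this point.
- **The margin is the wrong yardstick.** With centre rates in ratio 1:2:3 to 1:3:6, 95% of the simulated shifts lie within 0.55 to 1.02 points, close to the 0.99-point margin. A reader might infer that centre mix could decide non-inferiority. That does not follow. The shift is part of a sampling error of about 2.7–3.05 points that the interval already covers.
- **The 4–15% range is not a between-centre range.** Section 1 reports it as published incidence and attributes the spread to characteristics of patients and procedures. It also describes all three sites as high-volume tertiary hospitals. A nearly fourfold gap between them has no support in the documents.
- **Site variation is inferred.** Staple removal is left to the surgeon and concerns one arm only. Nothing says that discharge practice or dressing charges differ between hospitals. The effect on length of stay and cost is therefore plausible but not sized by the protocol.
- **An SAP may already adjust for centre.** It is not at hand, so one cannot say that no analysis of this trial accounts for centre. What can be said is that the tests written into section 3.9 do not.
- **Stratifying by centre has a price.** The trial is open-label, so site staff see their own allocations, and blocks run within a site are easier to guess than blocks pooled over three. Section 3.4 is also in the past tense, so allocation may be over.

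These points limit the size of the concern and move the remedy from the allocation list to the analysis. They do not remove the case for adjusting, which costs almost nothing.

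**Conclusion.** The point holds as a modest, cheaply corrected loss of efficiency. As stated, neither the allocation nor the tests in section 3.9 account for centre. There is no bias in expectation, the type I error is essentially unchanged, and the sample size is unaffected.

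For SSI the loss is about 0.5% of the variance of the arm difference at assumed centre rates of 4/6/8%, and about 4% at an extreme 4/4/15%. It is zero if the centres share one rate. For length of stay, operative time and cost it equals the share of variance that centre explains; 5–20% is an illustrative assumption. These figures also rest on assumed centre sizes. The documents do not support reading this as a threat to the validity of the randomisation or of the non-inferiority conclusion.

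**What to change.** In section 3.9:

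- Compare length of stay, operative time and cost with centre, approach and tumour location as covariates, for example in a linear model with robust standard errors. Where a rank test is preferred, use one stratified by centre.
- Keep the primary SSI test. Add, as supportive, a Mantel-Haenszel risk difference stratified by centre. Centre alone is enough: at the planning rates only about 152 × 0.058 + 152 × 0.010 ≈ 10 events are expected, too few to spread over 12 strata.
- Tabulate allocation by centre.

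The cost is a few lines of analysis, with no new patients and no change to the primary test.

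Only if allocation has not started, consider centre as a further stratification factor, keeping the block sizes variable and concealed. This gives 3 × 2 × 2 = 12 strata with about 304/12 ≈ 25 patients on average. Under the assumed 45/20/20/15% shares and equal centres, the smallest would hold about 0.15 × 304/3 ≈ 15. The price is some incomplete blocks and, in an open-label trial, assignments that are easier to predict within a site. If allocation has begun, keep the existing list.

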### **3.8 Sample size calculation**

Sample size was calculated in consultation with the department of Biostatistics, Seoul St. Mary's Hospital. The reference SSI rate following skin stapling in laparoscopic colorectal surgery was estimated at 5.8%, based on published literature (Lee CS et al, 2020). The non-inferiority margin was set at 0.99 percentage points (i.e., the absolute difference in SSI rate between the skin adhesive and stapling groups must not exceed 0.99% in favor of stapling for the tissue adhesive to be declared non-inferior).

Using a one-sided Z test (unpooled), one-sided alpha of 0.025, and power of 80%, the required sample size is 152 participants per group, for a total of 304 participants. No adjustment for anticipated dropout has been made because both interventions are applied at the time of surgery; however, a 10% safety margin may be considered at the interim review.

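### Allocation is stratified by approach and tumour location, but section 3.9 names only unstratified tests, so precision is lost to the extent that the strata are prognostic

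*Protocol*

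**What the plan says.** **Design.** Protocol section 3.4 fixes two stratification factors with two levels each, which gives four strata: "Allocation was stratified by surgical approach (laparoscopic vs robotic-assisted) and tumor location (colon vs rectum". It adds: "Within each stratum, block randomization with variable block sizes (4,6, and 8) ensured balance while minimizing predictability". Patients were randomised "the day before surgery in a 1:1 ratio to either the skin adhesive (Bond) or skin stapling (Stapler) group".

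**Analysis.** Section 3.9 names a method for each class of endpoint:

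- Primary: "The primary endpoint (SSI rate) will be analyzed using a one-sided Z test for the difference in proportions", with a 95% confidence interval, in both the per-protocol (PP) and intention-to-treat (ITT) populations.
- Continuous secondary: "Continuous secondary endpoints (VAS, length of stay, operative time, cost) will be compared using the" t-test or the Mann-Whitney U test.
- Categorical: "Categorical variables (complication rates, patient satisfaction categories, pathological stage) will be analyzed using the chi-square test" or Fisher's exact test.
- Significance level: "A two-tailed p-value of <0.05 will be considered statistically significant for all secondary comparisons".

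No stratified test, covariate-adjusted model or sensitivity analysis using approach or tumour location appears anywhere in the protocol. The sample size in section 3.8 also takes no account of strata: "one-sided alpha of 0.025, and power of 80%, the required sample size is 152 participants per group, for a total of 304 participants".

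**The concern.** Blocking within strata makes the arms nearly equal in their mix of approach and tumour location. Differences between strata therefore contribute almost nothing to the true sampling variability of the arm comparison. An unstratified standard error still counts those differences as noise. If the strata are related to the outcome, the reported standard error is larger than the real one, intervals are too wide and tests reject less often than their nominal level.

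What is at stake is precision and power, mainly for the continuous secondary endpoints (pain score, length of stay, operative time, cost). The design has already paid for this precision, and the stated analysis does not collect it. Validity is not at stake.

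**Working it through.** **1. The plan's own figure.** Inputs from section 3.8 and the sample size output that follows it: stapling SSI 0.058, adhesive SSI 0.010, margin 0.0099, one-sided alpha 0.025, 152 per group, unpooled Z test.

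- Variance term: 0.058 × 0.942 + 0.010 × 0.990 = 0.0645.
- SE = sqrt(0.0645 / 152) = 0.0206.
- Power = Φ((0.0099 + 0.048) / 0.0206 − 1.96) = 0.8023.

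The stated 152 per group and actual power of 0.80233 are reproduced, with no strata in the calculation.

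**2. Formula for the loss.** Let R² be the share of outcome variance explained by the four strata. With balance inside strata:

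- SE ratio (unstratified to true) f = 1 / sqrt(1 − R²).
- Actual two-sided level of a nominal 5% test = 2 × (1 − Φ(1.96 f)).
- Unadjusted power where the adjusted analysis has 80% = Φ(2.80 − 1.96 f).

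**3. Continuous secondary endpoints.** The protocol gives no standard deviations, stratum shares or stratum means, so R² is an assumption.

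| R² (assumed) | SE ratio | Actual level | Power (80% if adjusted) |
|---|---|---|---|
| 0 | 1.000 | 0.050 | 80% |
| 0.05 | 1.026 | 0.044 | 78.5% |
| 0.10 | 1.054 | 0.039 | 77% |
| 0.20 | 1.118 | 0.028 | 73% |
| 0.30 | 1.195 | 0.019 | 68% |
| 0.40 | 1.291 | 0.011 | 61% |

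At R² = 0.20, 304 patients analysed without strata give the reported precision of 304 × 0.80 ≈ 243 analysed with them.

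**4. Check by simulation.** N = 304, four strata with assumed shares of 45%, 25%, 15% and 15%, permuted blocks of 4, 6 and 8 within each, no treatment effect, 4,000 replicates per row:

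| R² | Unadjusted SE / empirical SD | t-test rejects | Mann-Whitney rejects | Stratum-adjusted model rejects |
|---|---|---|---|---|
| 0 | 0.998 | 4.9% | 5.0% | 4.9% |
| 0.096 | 1.063 | 3.8% | 3.7% | 4.8% |
| 0.225 | 1.115 | 3.0% | 3.0% | 5.3% |
| 0.386 | 1.275 | 1.0% | 1.1% | 5.2% |

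The formula holds. The rank test, which reports no standard error, shows the same conservatism. With non-prognostic strata, neither approach loses anything.

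**5. Primary endpoint.** For a binary outcome, R² = w(1 − w)(p_r − p_c)² / (p(1 − p)), where w is the rectal share and p_r and p_c are the SSI rates in rectum and colon. With p = 0.058, the denominator is 0.0546. Assume w = 0.35:

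- p_r = 0.09, p_c = 0.041: R² = 0.2275 × 0.049² / 0.0546 = 0.010; SE ratio 1.005.
- p_r = 0.12, p_c = 0.025: R² = 0.2275 × 0.095² / 0.0546 = 0.038; SE ratio 1.019.

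Taking instead a rectal share of 30% or 40%, a rectum-to-colon risk ratio of 1.5 to 4, and an overall rate of 5.8% or 3.4% (the mean of the two planning rates), R² is about 0.001 to 0.03 and the SE is overstated by about 0.1% to 1.7%. A simulation with SSI of 4% in colon and 9% in rectum could not distinguish the ratio from 1 (0.99).

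At the planning rates the 95% interval's half-width is 1.96 × 2.06 = 4.04 percentage points, so a 2% overstatement is worth about 0.08 points.

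**The case against.** **An unadjusted analysis after stratified randomisation is valid, and its error is on the safe side.** This stands. There is no bias and no excess of false positives, and for a non-inferiority claim a slightly wide interval makes a false claim less likely. The protocol also claims no power for the secondary endpoints. The point is therefore one of efficiency.

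**Adjustment is commonly left to the SAP, which is not shown.** This stands only in part. Section 3.9 does not exclude adjusted analyses, but it names unstratified tests outright, including for the primary endpoint. A SAP that followed it would carry the mismatch forward.

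**Stratifying SSI has its own difficulty.** This stands. At the planning rates 152 × 0.058 + 152 × 0.010 = 8.8 + 1.5 ≈ 10 infections are expected over four strata, so some strata may have none. A rule for sparse strata is needed.

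**Stronger readings that the documents do not support.**

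- A reader might infer that standard errors are definitely overstated, and most of all for operative time, length of stay and cost. The protocol has no data on how prognostic the strata are, so neither the size nor the ranking can be established. The ranking is plausible for operative time, which section 3.6.2 measures over the whole operation. It is doubtful for cost, which consists of dressing supply, service and frequency, because section 3.3.1 gives the adhesive arm no additional dressing and arm may matter far more than stratum.
- A reader might also infer that leaving out centre is part of the same error, since three hospitals take part. Centre is not a stratification factor, so the design creates no corresponding need to adjust for it. Chance imbalance between centres is already covered by the unadjusted test's error rate. Section 3.7 does not list centre among the collected variables.

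**Conclusion.** The mismatch between sections 3.4 and 3.9 is real and stands in the text. Its consequence is conditional: the named tests are conservative only as far as approach and tumour location predict the outcome.

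For continuous secondary endpoints the loss runs from nothing (R² = 0) to a standard error about 20% too large and an actual level of about 1.9% (R² = 0.30), all on assumed R². For SSI the overstatement stays under about 2% in every scenario tried, so neither the non-inferiority conclusion nor the 152 per group is materially affected. This is a minor point, worth correcting because the correction is nearly free.

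**What to change.** Amend section 3.9 before any unblinded analysis, so that the adjustment is prespecified:

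- **Continuous secondary endpoints:** a linear model with arm, approach and tumour location, or a van Elteren test stratified by the same factors where the data are skewed.
- **Categorical endpoints:** Mantel-Haenszel methods stratified by approach and location.
- **SSI:** a Mantel-Haenszel risk difference stratified by approach and location, with its 95% confidence interval, in both ITT and PP, and a rule fixed in advance for pooling sparse strata.
- **Sensitivity:** keep the unstratified tests now named in section 3.9 as sensitivity analyses.

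Adjustment for centre is optional and is not needed to correct this point.

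The cost is wording only. Both factors must be known to the randomisation system, which is the safer source: section 3.7 lists operative technique and type of resection but not tumour location by name. The sample size need not change.
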